### 1.4.4 Method for Categorical Data

Categorical data will be analyzed by using the Fisher's exact test or Chi-square test as

appropriate. Ordinal data will be analyzed by using Mantel-Haenszel chi-square test on given scores.

## 1.5 Method for Handling Missing Value

According to protocol, multiple imputation methods were planned to be done for efficacy evaluations using PROC MI of SAS. Since the sample size is relative small for both treatments, predictive model for multiple imputation is not realistic. Additional statistics on LOCF (Last Observation Carry Forward) data will be presented for by-visit efficacy analysis.

### 9.7.3. Missing Data

The method for handling missing data will be included in the statistical analysis plan. Every effort will be made to obtain required data at each scheduled evaluation from all patients who have been randomized in the study to minimize missing data. However, in the event when there are missing data the following imputation methods will be used. For efficacy evaluations, multiple imputation methods will be used to handle missing data and will be detailed in the SAP. This imputation method is a robust method to impute potential missing measurements. The imputation will be carried out in SAS version 9.4 or later using PROC MI.

## 1.6 Pharmacokinetics Analyses

Pharmacokinetics data will not be provided, and PK parameters will not be analyzed per sponsor's decision, and therefore it is not covered in the SAP.

## 2 Protocol Versions and Protocol Amendments

The first subject was enrolled on 3-Dec-2020, and the last subject is expected to be dismissed on 7-Oct-2021. All applied protocol and CRF versions are listed as below.

No.	Protocol Version	CRF Version	IRB Approval	FDA Approval
1	3.0, 20OCT2020	1.1, 12OCT2021	5-Nov-2020	3-Nov-2020
2	Amendment 1.0, 11MAY2021	1.0, 06SEP2021	24-May-2021	24-Jun-2021

### 3 Mock-up Tables and Figures

The Mock-up “TABLES and FIGURES” is planned according to ICH E3, in which relevant Clinical Study Report (CSR) section is 14. The words shadowed below are to be adjusted or repeated upon real data, or just for notification.

#### 3.1 Analysis of Continuous Data

For ANOVA / ANCOVA / T test (two sample t test) noted in the mock-up table, Wilcox\_t (Wilcoxon rank-sum test in t approximation) will be applied if normality assumption is not valid (p-value of Shapiro-Wilk normality test  $\leq 0.05$ ).

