9.3. SAMPLE SIZE DETERMINATION AND RATIONALE

A total of approximately 20 subjects will be randomized 1:1 in this study. The sample size is based on clinical judgment. No statistical power calculation is used to establish the sample size for this proof-of-concept study.

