**For CI and p-value (between groups):**

Wilcox\_t denotes Wilcoxon rank-sum test (Mann-Whitney U Test) in t approximation

Wilcox\_z denotes Wilcoxon rank-sum test (Mann-Whitney U Test) in z approximation

ANOVA denotes Treatment effect in ANOVA model

ANCOVA denotes Treatment effect in ANCOVA model

For 95% CI (HL), HL denotes CI using Hodges-Lehman for median

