## 14 TABLES AND FIGURES

- *The texts in shaded Italic are for programming note.*
- *Column of Study Site includes columns of {001-CARE, 002-CAR, Total}*
- *Column of Treatment Group includes columns of {CX-4945, SOC, Total}*
- *Column 'Difference' denotes pairwise comparison statistics.*
- *Multi-Selection means 'A subject may be counted in more than one category'*
- *Description in <...> will be presented according to data values.*
- *For column p-value: refer to Abbreviations of statistics in [Instructions and Abbreviations] above.*
- *For Groups Diff., §C = CX-4945, §S = SOC,*  
*T denotes two sample t test, W denotes Wilcox\_t (Wilcoxon rank-sum test in t approximation),*  
*C denotes Chi-Square test, F denotes Fisher's exact test*

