## 14.2.3 Nasopharyngeal Swab RT-PCR Result and SARS-CoV-2 Viral Load

### 14.2.3.1 SARS-CoV-2 Viral Clearance and Viral Load [copies/µL]

Population: Intent-to-Treat Population / Per-Protocol Population

Characteristics	Treatment Group	Difference	P-value
--Repeat Population: <See populations above>			
. Repeat Visit:			
Visit 1 (Screening), Baseline, Visit 4 (Day 8), Visit 6 (Day 14, EOT), Visit 7 (Day 28, F1), LOCF			
N (Missing)	XXX (XXX)		
Negative	XXX (XXX.X%)		
Positive	XXX (XXX.X%)		
N (Missing)	XXX (XXX)		0.XXXX
Mean (SD)	XXX (XXX)		
Median (IQR)	XXX (XXX)		
Q1~Q3	XXX~XXX		
Min~Max	XXX~XXX		
Repeat [Baseline to Visit] except Visit 1 (Screening) and Baseline			C/F
N (Missing)	XXX (XXX)	0.XXXX	
Positive to Negative#	XXX (XX.X%)		
Positive to Positive	XXX (XX.X%)		
Diff. between groups	§C - §S		
Difference (#)	XXX%		
95% CI (#)	XXX% ~XXX%a		
Repeat [Visit - Baseline] except Visit 1 (Screening) and Baseline			TW
N (Missing)	XXX (XXX)	0.XXXX	
Mean (SD)	XXX (XXX)		
Median (IQR)	XXX (XXX)		
Q1~Q3	XXX~XXX		
Min~Max	XXX~XXX		
For W, normality is not applied			
Groups Diff	§C - §S		
Median (Asymptotic SE)	XXX		
95% CI (HL)	XXX~XXX		
For T, normality is applied			
Groups Diff	§C - §S		
Mean (SD)	XXX (XXX)		
95% CI	XXX~XXX		

a denotes CI using normal approximation for binomial proportion of #  
 Viral Load > 25,000.00 copies/µL is estimated as 25,000.00 copies/µL.  
 Baseline is Visit 2 (Day 1) data, or is Visit 1 if Visit 2 (Day 1) is null

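### With about 10 patients per arm, the SAP's t approximation for the rank-sum test is conservative and can give p > 0.05 beside a Hodges-Lehmann 95% interval that excludes zero.

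*SAP*

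**What the plan says.** - **Choice of test.** SAP 3.1 replaces a planned t test, ANOVA or ANCOVA when Shapiro-Wilk gives p ≤ 0.05: "Wilcoxon rank-sum test in t approximation) will be applied if normality assumption is not valid".
- **Which version is used.** The abbreviations (Instructions and Abbreviations, item 8) define `Wilcox_t`, which "denotes Wilcoxon rank-sum test (Mann-Whitney U Test) in t approximation", and also `Wilcox_z`, the "Wilcoxon rank-sum test (Mann-Whitney U Test) in z approximation". The key in SAP section 14 settles the matter: "T denotes two sample t test, W denotes Wilcox", followed by the suffix `_t`. W is therefore the t version. No exact rank test is defined.
- **The interval beside it.** Where the rank test is used, the viral load (14.2.3.1), EQ-5D-5L (14.2.5.1), laboratory (14.3.2 to 14.3.6, continuous layout) and vital-sign (14.3.8) tables print a 95% interval for which "HL denotes CI using Hodges-Lehman for median". Some of these blocks also carry a row labelled "Median (Asymptotic SE"). The change-from-baseline blocks for laboratory tests and vital signs show the interval without that row.
- **Sample size.** Protocol 9.3: "A total of approximately 20 subjects will be randomized 1:1 in this study", and "No statistical power calculation is used to establish the sample size for this proof-of-concept study".
- **Not stated.** Neither document gives a significance level, says whether a continuity correction is applied, or says whether the Hodges-Lehmann limits are exact or asymptotic.

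**The concern.** At 10 v 10 the rank-sum statistic has an exact null distribution that is trivial to compute, so an approximation is not needed. Referring the standardised statistic to a t distribution with N − 1 = 19 degrees of freedom widens the tails and inflates p near 0.05. The Hodges-Lehmann interval is not inflated in this way, so p-value and interval in one table block can point in opposite directions. At stake are some power for skewed endpoints in a very small trial, and table blocks that a reader would take for a mistake. The SAP already falls back on an exact test (Fisher) for sparse categorical tables in 3.2, but has no counterpart for ranks.

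**Working it through.** The documents give no operating characteristic to reproduce, so this is a direct calculation.

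**Inputs.** 10 per arm (Protocol 9.3, about 20 randomised 1:1). Two-sided 5% is an assumption, inferred from the 95% intervals. No ties is an assumption. The continuity correction c is taken as 0.5 and as 0.

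**Null distribution.** There are C(20,10) = 184,756 equally likely rank allocations. The number giving each U follows from the recursion f(m,n,u) = f(m−1,n,u−n) + f(m,n−1,u). U has mean 10·10/2 = 50 and SD √(10·10·21/12) = √175 = 13.23.

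**p-values.** Exact: 2·P(U ≤ u). t approximation: 2·P(t₁₉ > (|u − 50| − c)/13.23). For example, at u = 22 with c = 0.5 the statistic is 27.5/13.23 = 2.079.

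| U | exact p | t approx., c = 0.5 | t approx., c = 0 |
|---|---|---|---|
| 21 | 0.0288 | 0.0443 | 0.0410 |
| 22 | 0.0355 | 0.0514 | 0.0477 |
| 23 | 0.0433 | 0.0596 | 0.0554 |
| 24 | 0.0524 | 0.0690 | 0.0642 |

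**True size.** This is the exact probability of each rejection region.
- t approximation, c = 0.5: rejects at U ≤ 21, size 2.9%.
- t approximation, c = 0: rejects at U ≤ 22, size 3.5%.
- Exact test: rejects at U ≤ 23, size 4.3%.

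**Other splits** (t approximation with correction / without / exact):
- 8 v 8: 2.8% / 2.8% / 5.0%
- 9 v 9: 3.2% / 3.2% / 4.0%
- 9 v 10: 2.8% / 3.5% / 4.4%
- 11 v 11: 3.4% / 3.4% / 4.7%

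**Interval.** The Hodges-Lehmann limits are the C-th smallest and C-th largest of the 100 pairwise differences. Asymptotic: C = 50 − 1.96 × 13.23 = 24.07, used as 24. Exact: the largest C with 2·P(U ≤ C − 1) ≤ 0.05 is also 24. Either way the interval excludes zero at U ≤ 23.

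**Where they conflict.** With the correction, at U = 22 and U = 23; without it, only at U = 23. If the rank test is applied, the chance under the null is 4.33% − 2.88% = 1.45% with the correction and 0.78% without.

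**Power of the planned procedure.** Simulated with 12,000 runs, with Shapiro-Wilk on pooled within-arm residuals (an assumption; the SAP does not say what is tested for normality), the t test unless rejected, and otherwise the rank test.
- Normal data, 1 SD shift: the rank test is used in about 5% of runs. Power is 55.9% (t approximation, corrected) v 56.2% (exact), a loss of 0.3 points. At 1.25 SD: 75.1% v 75.4%, also 0.3.
- Lognormal data, 1 SD shift on the log scale: the rank test is used in about 80% of runs. Power is 47.4% (corrected) or 50.5% (uncorrected) v 53.5% (exact), a loss of 6.1 or 3.0 points.

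Since exact rejection and exclusion of zero by the interval coincide at 10 v 10, those lost runs are also the runs in which p-value and interval would disagree.

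**The case against.** The case against is mostly about size, and much of it stands.

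- A reader might infer that a 5% test is simply being run at 2.9%. That needs a continuity correction the SAP does not mention, and 5% itself is inferred. No non-randomised rank test reaches 5% at 10 v 10, so the fair comparison is with 4.3%, a shortfall of 0.8 to 1.4 points. The figure also belongs to the rank-sum step alone. Simulations of the whole normality-then-test procedure under the null gave about 4.0% to 4.8% with the corrected version.
- A reader might infer a loss of about 7 points of power from comparing the two rank tests under a 1 SD normal shift (44.0% v 51.2%). Under SAP 3.1 the rank test would rarely be used on such data, so that comparison does not describe the plan.
- A reader might take the asymptotic SE row to mean that the interval is a normal-approximation one. The label is attached to the median, and the SAP leaves the interval's type open. At 10 v 10 it makes no difference.
- The conflict is confined to one or two values of U. At 9 v 10, without the correction and with the limit index (20.995) rounded down, it disappears.
- The consequence is limited. The primary endpoint is safety, the adverse-event tables carry no p-values, the time-to-event endpoints use the log-rank test, the trial is unpowered, and nothing in the SAP ties a conclusion to p < 0.05 on a rank test.

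What remains is that the approximation is conservative at every split checked, with or without the correction, and that the exact alternative costs almost nothing.

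**Conclusion.** The point holds as a minor, conservative inefficiency and a source of occasional inconsistency, graded as something to consider. At 10 v 10 the rank-sum step has size 2.9% to 3.5% against 4.3% exact. A p-value above 0.05 can stand beside an interval excluding zero at U = 23, and at U = 22 if a continuity correction is used. The power cost to the procedure is under 0.5 points for normal data and about 3 to 6 points for the lognormal case.

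These figures rest on a two-sided 5% level, equal arms of 10, no ties, and Shapiro-Wilk applied to pooled residuals. Ties are likely in some tables: viral load is capped at 25,000 copies/µL, and the EQ-5D-5L total is a sum of five item levels. The exact cut-offs are not shown for those. The documents do not support reading this as a threat to the primary safety assessment or as a route to false positive findings.

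**What to change.** In SAP 3.1, item 8 of the Instructions and Abbreviations, and the key in section 14, define W as the exact Wilcoxon rank-sum test and state that the Hodges-Lehmann 95% limits are the exact ones from the same procedure. State the significance level and sidedness in 3.1 as well. At 10 v 10 without ties, p-value and interval then share the rejection region U ≤ 23 and agree. With ties small differences may remain, and a table footnote should say so.

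The cost is one option in the SAS software already planned (Protocol 9.7) and three short text edits. No design, data collection or endpoint changes.

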
● To evaluate other Clinical Benefit of treatment with CX-4945 relative to the control arm	
● All-cause mortality status – the number of deaths occurred in each treatment group from Randomization (Day 1) through Day 60.● Number of patients hospitalized in each treatment group from Randomization (Day 1) to Day 45● Number of days to normalization of oxygen saturation level measured by pulse oximeter at Randomization (Day 1), Day 4, Day 8, Day 11, Day 14, Day 28 and Day 45 and categorized as <96% versus ≥96%.● Proportion of patients with disease progression or improvement in health status occurring from Randomization (Day 1) to Day 28. Disease progression is defined as change in patient health status assessment from item 7 to items 1- 6 and health improvement -as change from item 7 to item 8, evaluated by the ordinal NIAID 8- point Clinical Progression Outcomes scale – collected at every visit. from randomization (Day 1) through Day 45. An 8-category ordinal scale of patient health status ranges from:
1. Death;2. Hospitalized, on invasive mechanical ventilation or extracorporeal membrane oxygenation (ECMO);3. Hospitalized, on non-invasive ventilation or high flow oxygen devices;4. Hospitalized, requiring supplemental oxygen;5. Hospitalized, not requiring supplemental oxygen - requiring ongoing medical care (COVID-19 related or otherwise);

	
6. Hospitalized, not requiring supplemental oxygen - no longer requires ongoing medical care;7. Not hospitalized, limitation on activities and/or requiring home oxygen;8. Not hospitalized, no limitations on activities. 
• Changes in EQ-D5-5L (used as an indicator of symptom improvement) from Baseline (Day 1) to Day 8, 14, 28.

• To evaluate changes in inflammatory markers	
• Changes in plasma IL-6 level from Randomization (Day 1) to Day 4, Day 8, Day 11, and Day 14.• Changes in CRP, LDH, CPK, ferritin, D-dimer from randomization (Day 1) to Day 4, Day 8, Day 11, and Day 14.

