9.8.4. Study Outcome Assessment

For continuous variables data will be summarized by treatment using n, mean, SD, minimum and maximum values. For categorical variables data will be summarized by treatment using frequency and percentage. No inferential statistics are planned. The Safety population will be used for the analysis of safety outcomes.

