### 1.4.3 Method for Continuous Data

Demographics, baseline characteristics and continuous efficacy data will be analyzed by using two sample t test or Wilcoxon rank-sum test as appropriate. Net changes from pre-treatment laboratory test results and vital signs will be analyzed by using ANCOVA model with baseline value as covariate or Wilcoxon rank-sum test as appropriate.

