### 14.3.6 Laboratory Examination – Urinalysis

- 14.3.6.1 Urinalysis – <Item 1 and Unit>
- 14.3.6.2 Urinalysis – <Item 2 and Unit>
- 14.3.6.3 .... Refer to [Instructions and Abbreviations] of section 16 for the test terms

*<LB Layout 1: For Continuous Laboratory Test; Clinical relevance analyses will be excluded if not applicable>*

Population: Safety Population

Characteristics	Treatment Group	Difference	p-value
. Repeat Visit: No ‘Visit 1 (Screening)’ for IL-6: Visit 1 (Screening), Baseline, Adjusted Visit 3 (Day 4), Adjusted Visit 4 (Day 8), Adjusted Visit 5 (Day 11), Adjusted Visit 6 (Day 14, EOT), Visit 7 (Day 28, F1), Visit 8 (Day 45, F2)			
N (Missing)	XXX (XXX)		
Mean (SD)	XXX (XXX)		
Median (IQR)	XXX (XXX)		
Q1~Q3	XXX~XXX		
Min~Max	XXX~XXX		
		T/W <Baseline Only>	
		0.XXXX	

For W, normality is not applied <Baseline Only>

Groups Diff	§C - §S
Median (Asymptotic SE)	XXX
95% CI (HL)	XXX~XXX

Characteristics	Treatment Group	Difference	p-value
For T, normality is applied <Baseline Only>			
Groups Diff		§C - §S	
Mean (SD)		XXX (XXX)	
95% CI		XXX~XXX	
N (Missing)	XXX (XXX)		
Normal	XXX (XX.X%)		
NCS	XXX (XX.X%)		
CS (Medical History)	XXX (XX.X%)		
CS (Adverse Event)	XXX (XX.X%)		
. Repeat [Visit – Baseline] excluding Visit 1 (Screening) and Baseline			ANCOVA/W
N (Missing)	XXX (XXX)		0.XXXX
Mean (SD)	XXX (XXX)		
Median (IQR)	XXX (XXX)		
Q1~Q3	XXX~XXX		
Min~Max	XXX~XXX		
95% CI (WI)	XXX~XXXwt		
For W, normality is not applied			
Groups Diff		§C - §S	
95% CI (HL)		XXX~XXX	
For ANOVA, normality is applied	XXX (XXX)		
LsMean (SE)	XXX~XXX		
95% CI of LsMean			
Groups Diff. (T)		§C-§S	
Difference of LsMean		XXX	
95% CI of LsMean		XXX~XXX	
ANCOVA Model (p-value 0.XXXX) with effect Treatment (p-value 0.XXXX), Baseline (p-value 0.XXXX), Treatment*Baseline (p-value 0.XXXX).			
. Repeat [<Baseline> to <Visit>]			
N (Missing)	XXX (XXX)		
Relieved	XXX (XX.X%)		
Unchanged	XXX (XX.X%)		
Worsened (Medical History)	XXX (XX.X%)		
Worsened (Adverse Event)	XXX (XX.X%)		

For Item excluding IL-6 Baseline is Visit 2 (Day 1) data, or is Visit 1 if Visit 2 (Day 1) is null

For IL-6 Baseline is Visit 2 (Day 1) data

Refer to [Instructions and Abbreviations] of title pages for Transition of Clinical Relevance

**<LB Layout 2: For Categorical Urinalysis Test, including pH;  
 MHCHISQ for PH, C/F for else>**

Population: Safety Population

Characteristics	Treatment Group	p-value

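### Inflammatory markers are tested as raw change, with a normality test choosing the method marker by marker and visit by visit; a fixed log-scale ANCOVA would be consistent and, if the markers are skewed, more powerful

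*SAP*

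**What the plan says.** The protocol (section 3) lists as a secondary objective "To evaluate changes in inflammatory markers", with endpoints for IL-6 and "Changes in CRP, LDH, CPK, ferritin, D-dimer from randomization (Day 1) to Day 4, Day 8, Day 11, and Day 14". Protocol 9.8.4 states "No inferential statistics are planned"; SAP 1.4.1 departs from this and adds treatment comparisons.

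For laboratory changes, SAP 1.4.3 specifies "ANCOVA model with baseline value as covariate or Wilcoxon rank-sum test as appropriate". SAP 3.1 supplies the rule: the rank-sum test (t approximation) "will be applied if normality assumption is not valid (p-value of Shapiro-Wilk normality test" at or below 0.05). It does not say which variable is tested for normality: model residuals, pooled change, or change within arm.

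SAP 14.3.4 lists the inflammatory markers, and LB Layout 1 (printed under 14.3.6) is the table for continuous laboratory tests. Its tested variable is visit value minus baseline on the original scale. The ANCOVA branch reports LS-means and their difference. The Wilcoxon branch reports a group difference with a Hodges-Lehmann interval and no baseline covariate. No log or ratio scale appears. The layout footnote describes the ANCOVA as a model "with effect Treatment (p-value 0.XXXX), Baseline (p-value 0.XXXX), Treatment*Baseline", whereas SAP 1.4.3 names baseline as the only covariate.

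**The concern.** There are three linked difficulties.

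- **The method is chosen by the data.** Six markers at four post-baseline visits (Days 4, 8, 11 and 14) make 6 × 4 = 24 separate choices. An adjusted difference in means at one visit may sit beside an unadjusted Hodges-Lehmann shift at the next, for the same marker. These are different quantities and do not form a readable time course.
- **The scale may be inefficient.** If a marker is positive and right-skewed, raw change is dominated by patients with high baselines. The fallback then gives up baseline adjustment in just the cases where the switch fires most often.
- **The ANCOVA is not uniquely defined.** If the footnote's interaction is in the model and baseline is not centred, the p-value on the treatment term answers a question nobody is asking: the arm difference at a marker value of zero.

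At stake is the ability of a very small trial to show a marker effect if one exists, and the interpretability of the p-values that the SAP chose to add.

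**Working it through.** **Inputs from the documents.** Sample size: "A total of approximately 20 subjects will be randomized 1:1 in this study", so about 10 per arm. Model and switch rule: SAP 1.4.3, 3.1 and LB Layout 1. There is no planned power to reproduce: "No statistical power calculation is used to establish the sample size for this proof-of-concept study".

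**Inputs assumed, because the documents give none.** Lognormal markers; log-SD 0.5 to 1.5; log-scale correlation ρ between baseline and follow-up 0.3 to 0.8; true ratio of geometric means 0.25 to 0.7; two-sided 0.05. Shapiro-Wilk is applied to the ANCOVA residuals unless stated.

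**Step 1: log-scale ANCOVA by formula.** Power ≈ Φ(|ln ratio| / [SD·√(1−ρ²)·√(2/n)] − 1.96). At SD 1.0, ρ 0.6, ratio 0.4, n = 10 per arm: 0.916 / (0.8 × 0.447) − 1.96 = 0.60, so about 73%. This approximation runs a little high at such a small n; simulation gives 67%.

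**Step 2: planned rule without the interaction, by simulation, ratio 0.4.**

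| Case | Planned rule | Log ANCOVA | Relative loss |
|---|---|---|---|
| log-SD 1.0, ρ 0.6 | 37% | 67% | 1 − 37/67 = 45% |
| Low end of grid (log-SD 0.8–1.3, ρ 0.4–0.8) | 17% | 36% | 1 − 17/36 = 53% |
| High end of the same grid | 78% | 97% | 1 − 78/97 = 20% |

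Repeat runs with minor coding differences put the planned rule at 37% to 42% in the first case. The switch to Wilcoxon fired in roughly 40% to 82% of trials over this grid, so mixed methods within one marker are to be expected.

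**Step 3: how the loss depends on skew.** In a separate set of 1,500 trials per scenario, ρ was 0.3 to 0.7. Ratios were 0.25 to 0.7 at log-SD 0.5 and 0.8, and 0.25 to 0.5 above that. Monte Carlo error is about 1.3 points of power.

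| log-SD | Loss, Shapiro-Wilk on residuals | Loss, on pooled change |
|---|---|---|
| 0.5 | 2–21% | 1–18% |
| 0.8 | 23–39% | 29–41% |
| 1.0 | 31–49% | 36–53% |
| 1.3 | 47–59% | 53–65% |
| 1.5 | 41–62% | 49–67% |

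The unspecified target of the normality test therefore changes the answer by several points. At log-SD 1.0, ρ 0.5, ratio 0.35, power was 40% (residuals) or 34% (pooled), against 73% for log ANCOVA and 70% for rank ANCOVA.

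**Step 4: the footnote model.** Write change = a + b·T + c·B + d·T·B, with T the treatment indicator and B the baseline. The arm difference at baseline B is b + d·B, so testing b alone tests the difference at B = 0. In simulation that test alone has about 6–10% power. The whole rule with it has 21% power in the reference case, against 67%: a loss of 1 − 21/67 = 69%. Even with mild skew (log-SD 0.5, ratio 0.5) it was 26% against 95%, a loss of 1 − 26/95 = 73%.

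**Step 5: false positives.** Under no effect, the rule without the interaction rejected in about 3% to 5.5% of trials at log-SD 0.5 and 0.8. At log-SD 1.0 both forms of the rule and log ANCOVA were near 5%.

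**The case against.** The strongest reply is that the size of the loss is assumed throughout. Nothing in the documents says the markers are skewed, one log-SD range is applied to six different assays, and data generated as lognormal with a multiplicative effect favour the log-scale comparator by construction. That stands, and the figures must be read as conditional. It is softened by two facts: the SAP itself provides for non-normality, and rank ANCOVA, which does not depend on choosing the log scale, recovers most of the power in the same simulations.

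The endpoints are also secondary, in an unpowered proof-of-concept trial for which the protocol planned no inference, and the table already gives medians, quartiles and a Hodges-Lehmann interval. This limits the weight of the point. It does not excuse an ambiguous model once p-values are printed.

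The interaction may be meant only as a slope check. The layout's LS-mean difference, evaluated at mean baseline, has 48% power in the reference case even with the interaction fitted. So the low figure belongs to the treatment-term p-value read literally, and SAP 1.4.3 supports the simpler model.

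A reader might infer more than the documents support:

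- *That the plan always loses more than half the power.* Without the interaction this needs strong skew, roughly log-SD 1.3 or more; at 1.0 it is borderline.
- *That baseline is thrown away.* ANCOVA keeps it when the normality test passes, and the fallback still subtracts it.
- *That false positives are inflated.* They are not.

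**Conclusion.** The point holds as one of efficiency and interpretability. Three features are plain from the SAP: raw-scale change, a data-driven switch that can alter method and effect measure between visits, and a footnote model that disagrees with SAP 1.4.3.

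The power cost is conditional on lognormal markers with 10 per arm. At a ratio of 0.4 and log-SD 0.8 to 1.3 it is about 20% to just over half without the interaction, less with milder skew, and above 60% only if the footnote model is used with uncentred baseline and the treatment term is tested on its own. The primary safety objective is untouched. The change is worth making because it is cheap, not because the present plan would produce false conclusions.

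**What to change.** Before database lock, amend the SAP for the six markers:

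1. At every visit, fit ANCOVA of log(value) on treatment and log(baseline), with no Shapiro-Wilk switch and no interaction.
2. Report the ratio of geometric means (CX-4945 over SOC) with its 95% CI, keeping the raw-scale descriptive statistics already in the layout.
3. Keep Wilcoxon or, preferably, rank ANCOVA as a sensitivity analysis at all visits.
4. Remove Treatment*Baseline from the model that gives the treatment p-value, so that LB Layout 1 agrees with SAP 1.4.3. If a slope check is wanted, fit it separately and label it so.

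The cost is SAP wording and a log transform in the programs; no new data are needed. Results will be read as ratios rather than differences, and the gain in power depends on the markers being skewed. The gain in consistency does not.
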